- B. Dose 1×10^{11} vp (arm 2 and arm 5)
- C. Dose 2×10^{11} vp (arm 3 and arm 6)

The injection site will be covered with a sterile dressing and the participants will stay in observation per 4 hours, in case of immediate adverse events. Investigator will decide whether the participant can leave or need additional time in hospital monitoring.

All participants will be vaccinated with the same procedure and according to the same schedule of clinical record. A standard electronic case report forms (e-CRF) will be produced and filled in.

7.2. *Medical visit*

Medical visit will be carried out at the endpoints indicated in the schedule of procedures and will always include a check of medical history, physical examination, weight and height (at screening only), pulse, blood pressure, after 10 min rest in sitting position, and body temperature.

7.3. *Blood test and other analysis for monitoring safety*

Biological testing for monitoring safety will be carried out at the endpoints indicated in the schedule of procedures at the laboratory of the clinical centers that enroll volunteers and will include:

- A. Full Blood Count
- B. Urine analysis
- C. Biochemistry: Sodium, Potassium, , , Albumin, Liver Function Tests (ALT, ALP, Bilirubin total and fractionated), Renal function (Creatinine and BUN), lactate dehydrogenases (LDH), alkaline phosphatases (ALP)
- D. Diagnostic serology: HBsAg, HCV antibodies, HIV antibodies (specific consent will be gained prior to testing blood for these blood-borne viruses)
- E. Coagulation: aPTT (ratio), PT (ratio) and INR.

Urine will be tested for pH, Glucose Protein, Haemoglobin, Leukocyte esterase, Ketones, Bilirubin, Urobilinogen and Nitrites at screening. For female participants only, urine will be tested for beta-human chorionic gonadotrophin (β -HCG) at screening.

Participants presenting with respiratory symptoms consistent with COVID-19 infection will undergo to molecular test for SARS-CoV-2 and admitted to hospital in isolation room until a negative is available.

Additional safety blood tests may be performed if clinically relevant at the discretion of the medically qualified investigators.

Item	Time of the visit since vaccination									Type of intervention
	Scr	T0	D2	W1	W2	W4	W8	W12	W24	
Window (days)	≤ 21	0	0	±1	±1	±2	±4	±7	±14	
Informed consent	x									Procedures
Eligibility	x									
Vaccination		x								
AE reporting		x	x	x	x	x	x	x	x	
Diary card		A				B				
Medical history	x									

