9.1. Definitions

Adverse event (AE). (AE) is any untoward medical occurrence in a participant, which may occur during or after administration of the vaccine and does not necessarily have a causal relationship with the intervention. An AE can therefore be any unfavorable and unintended sign (including an abnormal laboratory finding), symptom or disease temporally associated with the study intervention, whether or not considered related to the study intervention.

Adverse reaction (AR). An AR is any untoward or unintended response to the vaccine. This means that a causal relationship between the vaccine and an AE is at least a reasonable possibility, i.e., the relationship cannot be ruled out. All cases judged by the reporting medical Investigator as having a reasonable suspected causal relationship to the vaccine (i.e. possibly, probably or definitely related to the vaccine) will qualify as adverse reactions.

Unexpected adverse reaction (UAR). An UAR is any untoward or unintended response to the vaccine, the nature and severity of which is not consistent with the information about the medicinal product in question set out in the investigator brochure (IB) or summary of product characteristics.

Serious adverse event (SAE). A SAE is an AE that results in any of the following outcomes, whether or not considered related to the study intervention.

- A. Death
- B. Life-threatening event (i.e., the participant was, in the view of the Investigator, at immediate risk of death from the event that occurred).
- C. Persistent or significant disability or incapacity (i.e., substantial disruption of one's ability to carry out normal life functions).
- D. Hospitalization, regardless of length of stay, even if it is a precautionary measure for continued observation.
- E. Significant medical intervention including surgery or administration of drugs (examples of such medical events include allergic reaction requiring intensive treatment in an emergency room or clinic, blood dyscrasias, or convulsions regardless eventual need of hospitalization)
- F. A grade ≥ 3 abnormalities on safety blood test according to Common Terminology Criteria for Adverse Events (CTCAE v.4 and MedDRA 12.1).

Serious adverse reaction (SAR). A SAE (expected or unexpected) that, is in the opinion of the reporting Investigator, believed to be possibly, probably or definitely due to the vaccine.

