Suspect unexpected serious adverse reaction (SUSAR). A severe adverse reaction, the nature and severity of which is not consistent with the information about the medicinal product in question set out in the investigator brochure (IB) or Summary of Product Characteristics.

9.2. *Solicited Adverse Reactions*

Solicited Adverse Reactions are those (foreseeable) AEs following vaccination with GRAd-COV2, and include injection site pain, erythema, warmth, swelling, pruritus, myalgia, arthralgia, headache, fatigue, fever, feverishness, malaise and nausea.

Solicited Adverse Reactions are grade as following:

- A. None: Symptom does not experience
- B. Mild: Short-lived or mild symptoms; medication may be required. No limitation to usual activity
- C. Moderate: Mild to moderate limitation in usual activity. Medication may be required but hospitalization is not required.
- D. Severe: Considerable limitation in activity. Invasive intervention or hospitalization is required.

We do not expect life threatening or fatal solicited adverse reactions in this study.

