9.8. Halting rules and study termination due to safety issue

Safety halting rules have been developed considering the fact that this is a *first-in-human* dose escalation study. Solicited adverse events are those listed as in section 9.2, occurring within the first 7 days after vaccination (day of vaccination and six subsequent days). Unsolicited adverse events are AE other than the solicited AEs occurring within the first 7 days, or any AEs occurring after the first 7 days after vaccination.

Enrolment of participants in one arm will be upheld if:

- A. Solicited local adverse events (site of injection): 2 or more vaccinations in a group are followed by the same severe solicited local adverse event beginning within 2 days after vaccination (day of

vaccination and one subsequent day) and persisting at severe for >48 hrs and these are deemed possibly, probably or definitely related to study interventions.

- B. Solicited systemic adverse events: If 2 or more vaccinations in a group are followed by the same severe solicited systemic adverse event beginning within 2 days after vaccination (day of vaccination and one subsequent day) and these are deemed possibly, probably or definitely related to study interventions.
- C. Unsolicited adverse events: If 2 or more vaccinations in a group are followed by the same serious unsolicited adverse event (including the same laboratory adverse event) and relation with vaccination cannot be immediately excluded.
- D. One participant with serious adverse event considered possibly, probably or definitely related to vaccination occurs
- E. Life-threatening condition when relation with study intervention cannot be immediately excluded.
- F. Death when relation with study intervention cannot be immediately excluded.

If a halting rule has been met, we will inform the regulatory authority. Moreover, before restarting enrollment the DSMB should exclude that AE has no immediate causal relation with the vaccine or that benefit of vaccination outweigh risk of further AE occurrence. In these latter case Ethical committee should be involved in the decision. Halting rules apply to one dose and the next higher one, so that if halting rule is met for the highest dose, only this arm is upheld. If halting is met for intermediate dose, two arms are held. If halting rule is met for the lowest dose all the study is stopped pending on the investigation of causal association between AE and vaccination (DSMB advice).

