#### 4.11.1 Adverse Events

Adverse events (AEs) will be coded using the Medical Dictionary for Regulatory Activities (MedDRA) Version 23.0.

An AE is any untoward medical occurrence in a study subject administered an IMP which does not necessarily have a causal relationship with this treatment. An AE can therefore be any unfavorable and unintended sign (including a clinically significant abnormal laboratory finding), symptom, or disease temporally associated with the use of an IMP, whether or not considered related to the IMP. Adverse events may include the onset of new illness and the exacerbation of pre-existing conditions.

Other untoward events occurring in the framework of a clinical study will be recorded as AEs, e.g. those occurring during treatment-free periods (including Screening or post-treatment Follow-up periods), in association with study-related procedures and assessments or under placebo.

Concomitant illnesses, which existed before entry into the clinical study, will not be considered AEs unless they worsen during the treatment period. Pre-existing conditions will be recorded as part of the subject's medical history.

A treatment-emergent adverse event (TEAE) is defined as an AE that begins or worsens in severity in 28 days after study drug administration.

Adverse event with 'No Relationship' or 'Unlikely Related' causality will be evaluated as not related (relationship = No), otherwise (including missing causality) AE will be evaluated as related (relationship = Yes).

Adverse events with completely unknown start dates will be considered as treatment-emergent for the tabulations and will be shown as NK in the listings. Partially complete AE dates will not be imputed in the listings and the available day, month and year components will be used to determine if an adverse event is treatment-emergent taking the first dosing date and end of study date as references.

Solicited adverse reactions are foreseeable AEs following vaccination with GRAd-COV2 including the following AEs: injection site pain, erythema, warmth, swelling, pruritus, myalgia, arthralgia, headache, fatigue, fever, feverishness, malaise and nausea. Solicited adverse reaction is recorded as such on the corresponding AE's eCRF.

Adverse events of special interest (AESI) are any grade  $\geq 3$  abnormalities on safety blood test according to Common Terminology Criteria for Adverse Events v.5.0 (CTCAE, see section [4.11.3](#)).

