#### **4.11.2 Deaths, Serious Adverse Events, and Other Significant Adverse Events**

A serious AE (SAE) is defined as an AE which fulfills one or more of the following criteria: is a medically significant event (examples of such medical events include allergic reaction requiring intensive treatment in an emergency room or clinic, blood dyscrasias, or convulsions regardless eventual need of hospitalization), is a congenital anomaly/birth defect, requires hospitalization or prolongation of existing hospitalization, causes persistent or significant disability or incapacity, is a life-threatening event or results in death. Serious adverse event is recorded as such on the corresponding AE's eCRF.

Separate AE listings will be provided for the following:

- Deaths;
- Serious AEs;

- TEAEs leading to study discontinuation.

Listings format will follow format described for adverse events in Section 4.11.1.

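### Protocol 9.2 ties a Severe solicited reaction to hospitalisation or invasive intervention, so halting rules A and B add nothing to rule D for 10 of 13 solicited terms; separately, protocol and SAP define a serious adverse event differently

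*Protocol*

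**What the plan says.** **Severity.** Protocol 9.2 lists 13 solicited terms and grades them None, Mild, Moderate or Severe. The last grade reads "Severe: Considerable limitation in activity. Invasive intervention or hospitalization is required". Moderate stops at moderate limitation without hospitalisation. Section 9.6 then points to Table 1, where erythema above 100 mm, swelling above 50 mm and fever above 39.0 are Severe with no reference to admission.

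**Seriousness.** Protocol 9.1 counts as an SAE, among other outcomes, "Hospitalization, regardless of length of stay, even if it is a precautionary measure for continued observation" (criterion D), significant medical intervention (criterion E), and grade 3 or higher "abnormalities on safety blood test according to Common Terminology Criteria for Adverse Events (CTCAE v.4 and MedDRA 12.1") (criterion F). Section 7.3 says that participants with respiratory symptoms consistent with COVID-19 are tested and "admitted to hospital in isolation room until a negative is available".

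**Halting.** Section 9.8 A and B need two related severe solicited events of the same kind; B reads "If 2 or more vaccinations in a group are followed by the same severe solicited systemic adverse event". Rule C needs two of the same serious unsolicited event, laboratory events included. Rule D needs one: "One participant with serious adverse event considered possibly, probably or definitely related to vaccination occurs".

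**SAP.** Section 4.11.2 states "A serious AE (SAE) is defined as an AE which fulfills one or more of the following criteria", then gives a list with no laboratory-grade criterion and no precautionary clause, and adds congenital anomaly. It takes seriousness from the eCRF. In SAP 4.11.1 the same laboratory values appear under another label: "Adverse events of special interest (AESI) are any grade" 3 or higher on a safety blood test, by CTCAE v5.0.

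**Endpoint E.** The protocol synopsis calls it *severe* AE; section 4.2.1 calls it *serious* AE.

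**The concern.** Severity (how intense) and seriousness (what outcome) should be separate scales. Here the Severe grade in 9.2 is defined by an outcome that 9.1 already makes serious. A rule that waits for two severe events then sits behind a rule that acts on one serious event.

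The consequences are practical. Rule D acts on the dose and the next higher one, and at the lowest dose it stops the whole study pending investigation, so it matters which events reach it. Two scales for the same reaction also mean that primary endpoints A and B can be graded differently by different sites. Endpoint E, a primary safety endpoint, can give different counts from the same events, depending on whether a site follows protocol 9.1 or the SAP text.

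**Working it through.** The plan states no halting probability and no sample-size figure to reproduce; its only arithmetic is 6 arms × (3 + 12) = 90.

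**Step 1. Solicited terms against Table 1**

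| Type | Terms in 9.2 | With a Table 1 row | Graded by 9.2 only |
|---|---|---|---|
| Local (rule A) | pain, erythema, warmth, swelling, pruritus | erythema, swelling | 3 of 5 |
| Systemic (rule B) | myalgia, arthralgia, headache, fatigue, fever, feverishness, malaise, nausea | fever | 7 of 8 |
| All | 13 | 3 | 10 of 13 |

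**Step 2. Rules A and B against D.** For the 10 terms, Severe requires hospitalisation (9.1 D) or invasive intervention, which I read as significant medical intervention (9.1 E). Each such event is an SAE. A, B and D use the same causality test (possibly, probably or definitely related). The first case therefore meets D, and the second, needed for A or B, changes nothing. For erythema, swelling and fever, Table 1 allows a severe event that is not serious, so A and B can act alone. If 9.2 governed these too, all 13 terms would fall inside D.

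**Step 3. Rule C against D.** C already says *serious*, so its overlap with D does not come from the Severe grade. For events judged related, one case meets D before two meet C. Criterion F extends this to grade 3 or higher laboratory values. C's causality test (relation cannot be immediately excluded) is not the same as D's, so C may still act before causality is assigned.

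**Step 4. What one case instead of two means.** The documents give no event rate. I assume a per-participant rate p of 1%, 5% or 10%. *Group* in 9.8 could mean 3, 12 or the arm of 15.

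P(at least 1) = 1 − (1−p)^n; P(at least 2) = 1 − (1−p)^n − np(1−p)^(n−1).

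| n | p = 1% | p = 5% | p = 10% |
|---|---|---|---|
| 3 | 3.0% vs 0.03% | 14.3% vs 0.7% | 27.1% vs 2.8% |
| 12 | 11.4% vs 0.6% | 46.0% vs 11.8% | 71.8% vs 34.1% |
| 15 | 14.0% vs 1.0% | 53.7% vs 17.1% | 79.4% vs 45.1% |

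Each cell is the one-case trigger against the two-case trigger. Example: n = 15, p = 5%: 1 − 0.95^15 = 53.7%.

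**Step 5. How much of A/B is already D.** Let s be the share of severe events that are also serious, and treat all severe events as the same term. The chance that A/B is met without D is (1−ps)^n − (1−p)^n − np(1−s)(1−p)^(n−1). For n = 15 and p = 2%, 5%, 10%:

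| s | Share of A/B triggers already met by D |
|---|---|
| 1 (9.2 governs all terms) | 100% |
| 10/13 (term count as a proxy) | 95.0%, 95.6%, 96.5% |
| 0.5 | 76.1%, 77.9%, 81.0% |
| 0 | 0% |

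The result depends on s, which the documents do not fix.

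**Step 6. SAE definitions side by side**

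| Item | Protocol 9.1 | SAP 4.11.1–4.11.2 |
|---|---|---|
| Hospitalisation | any, precautionary included | required or prolonged; no precautionary clause |
| Grade 3+ laboratory value | SAE | AESI; not in the SAE list |
| CTCAE | v4 | v5.0 |
| Congenital anomaly | not listed | SAE |
| Source of the flag | investigator's report | eCRF field |

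A site that flags by 9.1 puts a grade 3 laboratory value in both the SAE and the AESI outputs. A site that flags by the SAP text puts it in AESI only. The isolation admissions in 7.3 are SAEs under 9.1 D whatever the test shows.

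**Step 7. Scale of the laboratory criterion.** Assume a chance r of a grade 3+ value at each of the 7 post-vaccination visits, independent across visits. Expected participants affected = 90 × [1 − (1−r)^7], which is 0.6, 3.1 or 6.1 for r = 0.1%, 0.5% or 1%.

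**The case against.** **Rules A to C are not redundant as a set.** A reader might infer that they are. Table 1 gives three solicited terms a severe grade without admission, and rule C has its own wording and causality test. This stands, and limits the claim to 10 of 13 terms for A and B, and to related events for C.

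**The DSMB is not left without a threshold.** Rules A to F are alternatives, and meeting any one holds enrolment. Overlap errs towards halting, and section 9.5 also suspends enrolment for a serious adverse reaction within week 10. This stands: the fault is rules without effect and conflicting definitions, not absence of protection.

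**Reactogenicity is not shown to be biased downwards.** That inference is tempting, but considerable limitation at home fits neither Moderate nor Severe, so the direction depends on what each site chooses. Diary severity is also summarised (SAP 4.12.1), on a scale that the documents do not show. What remains is a grading gap.

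**Laboratory values are not lost.** It would be wrong to say that none can be an SAE in the SAP outputs: the SAP uses the eCRF flag, and it also reports these values as AESI and by CTCAE grade. The problem is an undetermined label and possible double counting.

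**The versions may differ.** The SAP rests on Protocol Version 2.0 and places the laboratory tests in protocol section 8.3; here they are in 7.3. The screening window in the schedule (28 against 21 days), the ECG row and the diary returns differ too. Part of the SAP mismatch may come from this. The conflicts inside the protocol do not.

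**The synopsis wording may be a slip.** Probably so, since 4.2.1 and 9.5 are clear. It still needs correcting, because it names a primary endpoint.

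**Conclusion.** The point holds in a limited form. Within the protocol, 9.2 conflicts with 9.6 and Table 1, and considerable limitation managed at home has no grade. Rules A and B have no independent effect for 10 of 13 solicited terms (3 of 5 local, 7 of 8 systemic), but keep one for erythema, swelling and fever. Rule C is pre-empted by D for events judged related. These conclusions follow from the text; for A and B, the only reading required is that invasive intervention in 9.2 counts as significant medical intervention in 9.1.

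Between protocol and SAP, the endpoint E count depends on which SAE definition sites apply, and one event may be counted as both SAE and AESI. This rests on the two documents being meant to match, which must be confirmed.

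The size cannot be derived. Every rate in steps 4, 5 and 7 is an assumption, and the figures show only how far the result could move. The documents do not establish a direction of bias in reactogenicity.

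**What to change.** 1. The sponsor and the DSMB should reconcile protocol 9.1, 9.2, 9.6 with Table 1, and 9.8 A to D, so that each event has one grade and each rule its intended role. No grade, threshold or halting rule is proposed here.
2. Confirm which protocol version the SAP implements. Then use one SAE definition and one CTCAE version in the protocol, SAP and eCRF, and state whether grade 3 or higher laboratory values are SAE, AESI or both.
3. Name endpoint E *serious* in the synopsis.
4. In the SAP, tabulate SAEs by seriousness criterion, with laboratory grade only and protocol-mandated admission only as separate rows. Run the table to week 24, as endpoint E does; the SAP's SAE overview counts treatment-emergent events, which have a 28-day window.

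The cost is a protocol clarification, some SAP wording and one extra table. The seriousness criterion must be recorded on the SAE form.

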9.3. Assessment of causality

For every AE, an assessment of the relationship of the event to the administration of the vaccine will be undertaken by the doctors who have enrolled the participants. An intervention-related AE refers to an AE for which there is a probable or definite relationship to administration of a vaccine. An interpretation of the causal relationship of the intervention to the AE in question will be made, based on the type of event; the relationship of the event to the time of vaccine administration; and the known biology of the vaccine. Alternative causes of the AE, such as the natural history of pre-existing medical conditions, concomitant therapy, other risk factors and the temporal relationship of the event to vaccination will be considered and investigated.

Causality assessment will take place during planned safety reviews by DSMB.

9.4. Guidance for assessing relationship of AE with vaccination

- A. No Relationship. No temporal relationship to vaccine and alternative etiology (clinical state, environmental or other interventions); and it does not follow known pattern of response to the vaccine.
- B. Unlikely. Unlikely temporal relationship to study product and alternative etiology likely (clinical state, environmental or other interventions) and it does not follow known typical or plausible pattern of response to study product.
- C. Possible. Reasonable temporal relationship to study product; or event not readily produced by clinical state, environmental or other interventions; or similar pattern of response to that seen with other vaccines
- D. Probable. Reasonable temporal relationship to study product; and event not readily produced by clinical state, environment, or other interventions or known pattern of response seen with other vaccines
- E. Definite. Reasonable temporal relationship to study product; and event not readily produced by clinical state, environment, or other interventions; and known pattern of response seen with other vaccines.

